7 CONCURRENT MEDICATIONS

All subjects should be maintained on the same medications throughout the entire study period, as medically feasible, with no introduction of new chronic therapies. Specific allowed and disallowed medications are detailed in Section 6 (Eligibility Criteria).

8 STUDY TREATMENTS

8.1 Method of Assigning Subjects to Treatment Groups

All consenting and qualified participants will be assigned to the single treatment arm.

8.2 Blinding

Neither participants nor study investigators will be blinded to the study intervention.

8.3 Formulation of Test and Control Products

We will administer labeled D₆-25(OH)D₃ Solution for Injection, 20 µg/mL intravenously. D₆-25(OH) D₃ Solution for Injection, 20 µg/mL has been manufactured according to current Good Manufacturing Practices by SRI International (Palo Alto, CA).

8.3.1 Formulation of Test Product

The labeled D₆-25(OH)D₃ Solution for Injection, 20 µg/mL prepared by SRI International is formulated in cosolvents to enhance solubility. Each mL contains 20 µg D₆-25(OH) D₃, 60% propylene glycol (60%), 10% ethanol (ETOH) and water (30%) for injection, to volume.

8.3.2 Packaging and Labeling

The formulated drug product has been aliquoted into single-use vials by SRI International and frozen at <60°C for storage. Vial labels include the drug product name, concentration, batch number, manufacture date, and storage conditions, similar to the draft label shown below.

D₆-25-Hydroxyvitamin D₃ Solution for Injection, 20 µg/mL, 5 mL single use vial
 
Subject ID: _____
 
Batch No.: 16504-08 Manuf. Date: Sept 2016
 
Store at ≤ -60°C (- 76°F)
 
See protocol for preparation for administration instructions
 
Caution: New Drug -- Limited by Federal (US) law to investigational use. Keep out of the reach of children.
 
Manufactured by SRI International, Menlo Park, CA 94025

--

8.4 Supply of Study Drug at the Site

Single-use vials will be stored at <60°C at the University of Washington Investigational Drug Services or Kidney Research Institute. Individual doses of D₆-25(OH) D₃ Solution for Injection will be prepared for intravenous administration by the University of Washington Investigational Drug Services by thawing and drawing the appropriate volume into a syringe. The prepared dose of will be calculated according to estimated blood volume based on body weight. The prepared dosing syringe will be labeled with the participant's full name, date of birth, and medical record number along with the drug contents. Once thawed, the drug product will be infused within eight hours of preparation.

8.4.1 Dosage/Dosage Regimen

Each participant will receive a single intravenous dose of D₆-25(OH) D₃ Solution for Injection, 20 µg/mL. We will use estimated blood volume based on body weight to achieve a target concentration of 5 ng/mL D₆-25(OH) D₃. The target of 5 ng/mL was selected because it will allow precise tracking of circulating deuterated D₆-25(OH) D₃ concentration throughout follow-up (based on known limits of detection for our assay) without substantially perturbing underlying vitamin D status. Theoretically, the dose required to achieve a 5 ng/mL increment in deuterated 25(OH)D₃ concentration can be calculated as the targeted peak concentration multiplied by the volume of distribution, which for 25(OH)D₃ is expected to be equal to blood volume. We will use the formula of Nadler et al (1962) to estimate blood volume for each participant. We will begin the study by administering to each participant a dose of 5 ng/mL x estimated blood

volume. A typical dose would be 32 µg (1.6 mL) for an 85 kg individual. We will monitor achieved D₆-25(OH) D₃ concentrations throughout the course of the study. If our initial approach fails to achieve peak D₆-25(OH) D₃ concentrations near 5 ng/mL, we will revise our approach for future participants, as indicated. For example, if mean peak achieved 25(OH)D₃ concentrations are near 2.5 ng/mL with our initial approach, we will increase our dose by a factor of two. We will not exceed a dose of 100 µg (5 mL) D₆-25(OH) D₃ for any participant.

8.4.2 Dispensing

All study drug will be dispensed by the University of Washington Investigational Drug Services.

8.4.3 Administration Instructions

The study drug will be administered intravenously on a single occasion over a period of 5 minutes. Subsequent to thawing, the drug product vial may be stored refrigerated (2-8 °C) for up to 24 hours prior to preparation for administration in a syringe. Once prepared for administration and held at room temperature, the solution should be administered within 8 hours.

8.5 Supply of Study Drug at the Site

All single-use vials of formulated D₆-25(OH)D₃ will be shipped overnight on dry ice to the University of Washington Investigational Drug Services, with temperature monitoring. The University of Washington is the sole clinical site for this study.

8.5.1 Storage

Study drug will be securely stored at a temperature <-60°C at the University of Washington Investigational Drug Services or Kidney Research Institute.

8.6 Study Drug Accountability

An accurate and current accounting of the dispensing and return of study drug for each subject will be maintained on an ongoing basis by the University of Washington Investigational Drug Services. The number of study drug dispensed and returned by the subject will be recorded on the Investigational Drug Accountability Record.

8.7 Measures of Treatment Compliance

Each study drug administration will be directly observed by study staff.

9 STUDY PROCEDURES AND GUIDELINES

A Schedule of Events representing the required testing procedures to be performed for the duration of the study is provided in Section 10 (Evaluations by Visit) below and diagrammed in Appendix 1.

Prior to conducting any study-related activities, written informed consent and the Health Insurance Portability and Accountability Act (HIPAA) authorization must be signed and dated by the subject or subject's legal representative. If appropriate, assent must also be obtained prior to conducting any study-related activities.

9.1 Clinical Assessments

9.1.1 Concomitant Medications

All concomitant medication and concurrent therapies will be documented at Screening, Baseline (Study Day 0), and the final Study Visit (Study Visit 10). Dose, route, unit frequency of administration, and indication for administration and dates of medication will be captured.

9.1.2 Demographics

Demographic information (date of birth, gender, race) will be recorded at Screening.

9.1.3 Medical History

Relevant medical history, including history of current disease, other pertinent history, and information regarding underlying diseases will be recorded at Baseline (Study Day 0).

9.1.4 Physical Examination

Height and weight will be measured at the Screening visit and at Baseline (Study Day 0). When prompted by reports or suspicion of potential adverse effects during follow-up, physical exam findings will be documented by qualified staff (MD, NP, RN, or PA) and will be followed by a physician or other qualified staff immediately or at the next scheduled visit, as indicated.

9.1.5 Vital Signs

Body temperature, blood pressure, pulse and respirations will be measured after resting for 5 minutes at Baseline (Study Day 0), prior to administration of study drug.

9.1.6 Other Clinical Procedures

Physical activity will be ascertained by questionnaire and accelerometry between Study days 1 and 7. Vitamin D intake will be estimated by food frequency questionnaire at Baseline. Serum and plasma will be collected at Baseline to measure calcium and phosphorus, intact parathyroid hormone, fibroblast growth factor-23, and vitamin D binding protein. Two 24-hour urine collections will be obtained, immediately preceding and following administration of D₆-25(OH) D₃, to quantify urinary excretion of albumin and the metabolites of deuterated D₆-25(OH) D₃, respectively. Dialysis patients will be exempt from all urine collections. Adiposity will be measured by Dual energy X-ray absorptiometry at the baseline visit.

9.1.7 Adverse Events

Information regarding occurrence of adverse events will be captured throughout the study. Duration (start and stop dates and times), severity/grade, outcome, treatment and relation to study drug will be recorded on the case report form (CRF).

9.2 Clinical Laboratory Measurements

9.2.1 Hematology

A complete blood count will be obtained at the Screening Visit.

9.2.2 Blood Chemistry Profile

Serum sodium, potassium, chloride, bicarbonate, random glucose, BUN, creatinine, aspartate aminotransferase (AST/SGOT), alanine aminotransferase (ALT/SGPT), albumin, calcium, and phosphorous will be obtained at the Screening Visit.

Repeat serum sodium, potassium, chloride, bicarbonate, random glucose, BUN, creatinine, aspartate aminotransferase (AST/SGOT), alanine aminotransferase (ALT/SGPT), albumin, calcium, and phosphorous will be obtained at Baseline and Study Day 7.

Intact parathyroid hormone (PTH) will be measured at Visits 2 and 5 (Day 0 and 7 gauged from administration of deuterated 25(OH)D₃).

9.2.3 Pregnancy Test

A urine pregnancy test will be obtained from female subjects who are of childbearing age at the Baseline Visit prior to administration of the study drug. For anuric (dialysis) participants, blood pregnancy tests will be obtained to rule out pregnancy during the week preceding the administration of the study drug.

9.3 Pharmacokinetic Measurements

Blood for determination of serum concentrations of deuterated 25(OH)D₃ and its metabolites will be collected at Study Visits 2-10.

At Baseline, blood will be drawn prior to administration of study drug as well as 5 minutes and 4 hours after administration.

9.4 Research Laboratory Measurements

Novel products of 25(OH)D₃ catabolism, including 4β,25(OH)₂D₃ and 25(OH)D₃-3-sulfate will be measured using LC-MS/MS, as previously described.⁵⁷ 25(OH)D₃-3-sulfate will be extracted from plasma.

10 EVALUATIONS BY VISIT

10.1 Screening Visit (Study Visit 1)

The following activities will occur during the screening visit:

- Collect signed consent form
- Perform focused medical history restricted to study eligibility criteria
- Complete medication inventory through EMR and patient report.
- Physical Exam (height and weight), and Vital Signs (blood pressure, heart rate)
- Collect non-fasting blood sample for measurement of complete blood count and total 25(OH)D.
- Collect non-fasting blood sample for serum sodium, potassium, chloride, bicarbonate, random glucose, BUN, creatinine, AST/SGOT, ALT/SGPT, albumin, calcium, and phosphorous.
- Collect urine for measurement of albumin and creatinine (except for hemodialysis patients).
- Participants who meet eligibility criteria at the screening visit will be invited to return for the remaining study visits.
- Provide selected subjects with supplies required for first 24-hour urine collection

10.2 Baseline Visit (Study Visit 2, Day 0)

Visit 2 will take place at the University of Washington Clinical Research Center (CRC) or a suitable alternate facility and will last approximately 5 hours. Visit 2 will take place no more than 90 days after Visit 1. If more than 90 days elapse between Visits 1 and 2, screening procedures may be repeated to verify continued eligibility. The following activities will occur during the baseline visit:

- Perform a complete medical history
- Review current medications.
- Physical Exam (height and weight), and Vital Signs (blood pressure, heart rate)
- Complete physical activity and food frequency questionnaires.
- Pregnancy test for women of childbearing potential
- Collect blood **prior to administration of study drug** for measurement of basic chemistries, vitamin D metabolites, parathyroid hormone (PTH), and other measurements related to kidney disease and vitamin D metabolism.
- Collect urine sample from first 24-hour collection period. Sample will be used for measurement of albumin, creatinine, vitamin D binding protein, and vitamin D metabolites:
- Perform dual energy x-ray absorptiometry (DEXA) to measure adiposity.
- Administer D₆₋₂₅(OH) D₃ intravenously.
- Collect blood 5 minutes and 4 hours post-infusion for measurement of vitamin D metabolites.
- Distribute supplies for second 24-hour urine collection.

10.3 Study Visit 3 (Day 1)

This visit is expected to last less than one hour. The following activities will occur during Visit 3:

- Collect urine sample from second 24-hour collection period.
- Collect blood for measurement of serum vitamin D metabolite concentrations.
- Distribute Accelerometer for measurement of physical activity

10.4 Study Visit 4 (Day 4)

This visit is expected to last less than one hour. A window of one day before or after the scheduled date will be allowed when needed. Blood will be collected for measurement of serum vitamin D metabolite concentrations.

10.5 Study Visit 5 (Day 7)

This visit is expected to last less than one hour. A window of one day before or after the scheduled date will be allowed when needed. The following activities will occur during Visit 7:

- Collect blood for measurement of serum vitamin D metabolite concentrations.
- Collect blood for serum sodium, potassium, chloride, bicarbonate, random glucose, BUN, creatinine, aspartate aminotransferase (AST/SGOT), alanine aminotransferase (ALT/SGPT), albumin, calcium, and phosphorous at Study Visit 5 (Day 7) to monitor study safety.
- Collect Accelerometer

10.6 Study Visits 6-10 (Day 14, 21, 28, 42, and 56)

Each of these visits is expected to last less than one hour. A window of up to 3 days before or after the scheduled date will be allowed when needed. Blood will be collected at each visit for measurement of serum vitamin D metabolite concentrations. Medication inventory will be repeated at Visit 10 (Day 56).

11 ADVERSE EXPERIENCE REPORTING AND DOCUMENTATION

11.1 Adverse Events

An adverse event (AE) is any symptom, sign, illness or experience that develops or worsens in severity during the course of the study. Intercurrent illnesses or injuries should be regarded as adverse events. Abnormal results of diagnostic procedures are considered to be adverse events if the abnormality:

- results in study withdrawal
- is associated with a serious adverse event
- is associated with clinical signs or symptoms
- leads to additional treatment or to further diagnostic tests
- is considered by the investigator to be of clinical significance

11.1.1 AE Severity

The National Cancer Institute's Common Terminology Criteria for Adverse Events (CTCAE) Version 3.0 should be used to assess and grade AE severity, including laboratory abnormalities judged to be clinically significant. The modified criteria can be found in the study manual. If the experience is not covered in the modified criteria, the guidelines shown in Table 11.1 below should be used to grade severity. It should be pointed out that the term "severe" is a measure of intensity and that a severe AE is not necessarily serious.

Table 11.1 AE Severity Grading

Severity (Toxicity Grade)	Description
Mild (1)	Transient or mild discomfort; no limitation in activity; no medical intervention or therapy required. The subject may be aware of the sign or symptom but tolerates it reasonably well.
Moderate (2)	Mild to moderate limitation in activity, no or minimal medical intervention/therapy required.
Severe (3)	Marked limitation in activity, medical intervention/therapy required, hospitalizations possible.
Life-threatening (4)	The subject is at risk of death due to the adverse experience as it occurred. This does not refer to an experience that hypothetically might have caused death if it were more severe.

11.1.2 AE Relationship to Study Drug

The relationship of an AE to the study drug should be assessed using the following the guidelines in Table 11.2.

Table 11.2 AE Relationship to Study Drug

Relationship to Drug	Comment
Definitely	Previously known toxicity of agent; or an event that follows a reasonable temporal sequence from administration of the drug; that follows a known or expected response pattern to the suspected drug; that is confirmed by stopping or reducing the dosage of the drug; and that is not explained by any other reasonable hypothesis.
Probably	An event that follows a reasonable temporal sequence from administration of the drug; that follows a known or expected response pattern to the suspected drug; that is confirmed by stopping or reducing the dosage of the drug; and that is unlikely to be explained by the known characteristics of the subject's clinical state or by other interventions.
Possibly	An event that follows a reasonable temporal sequence from administration of the drug; that follows a known or expected response pattern to that suspected drug; but that could readily have been produced by a number of other factors.
Unrelated	An event that can be determined with certainty to have no relationship to the study drug.

11.2 Serious Adverse Experiences (SAE)

An SAE is defined as any AE occurring at any dose that results in any of the following outcomes:

- death
- a life-threatening adverse experience
- inpatient hospitalization or prolongation of existing hospitalization
- a persistent or significant disability/incapacity
- a congenital anomaly/birth defect

Other important medical events may also be considered an SAE when, based on appropriate medical judgment, they jeopardize the subject or require intervention to prevent one of the outcomes listed.

A serious adverse event is any AE that is:

- fatal
- life-threatening
- requires or prolongs hospital stay
- results in persistent or significant disability or incapacity
- a congenital anomaly or birth defect
- an important medical event

Important medical events are those that do not fit the other definitions of serious adverse events, but the event may jeopardize the patient and may require treatment to prevent one of the listed serious adverse events.

Adverse events will be collected if they occur between the time of informed consent and up to 30 days after the last study visit. All unresolved adverse events will be followed by the PI until resolution, the adverse event is otherwise explained, or the participant is lost to follow-up. At the last study visit, the investigator will instruct each participant to report any subsequent event that the participant, or participant's personal physician, reasonably believes may be related to the study. The investigator will notify the study sponsor of any death or adverse event occurring after the participant has discontinued participation if the event can be reasonably related to the study.

11.3 Abnormal lab values

An abnormal clinical laboratory value will be documented as an adverse event if one of the following applies:

1. The abnormality is not contradicted by a repeat test to confirm the abnormality.
2. The abnormality suggests a disease and/or organ toxicity.
3. The abnormality is of a degree that requires active management (e.g., requires a medication change, more frequent follow-up, or further diagnostic evaluation).

11.4 Hospitalization, Prolonged Hospitalization or Surgery

Any adverse event that results in hospitalization or prolonged hospitalization will be documented and reported as a serious adverse event unless specifically instructed otherwise in this protocol. Any condition responsible for surgery will be documented as an adverse event if the condition meets the criteria for an adverse event. Neither the condition, hospitalization, prolonged hospitalization, nor surgery are reported as an adverse event in the following circumstances:

1. Hospitalization or prolonged hospitalization for diagnostic or elective surgical procedures for a preexisting condition. Surgery should not be reported as an outcome of an adverse event if the purpose of the surgery was elective or diagnostic and the outcome was uneventful.
2. Hospitalization or prolonged hospitalization required to allow efficacy measurement for the study.
3. Hospitalization or prolonged hospitalization for therapy of the target disease of the study, unless it is a worsening or increase in frequency of hospital admissions as judged by the clinical investigator.

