CONCOMMITANT MEDICATIONS	
Allowed:
 
 Vitamin D supplements (cholecalciferol, ergocalciferol) not to exceed a mean daily dose of 400 IU, within 3 months (wash-out allowed) 
Prohibited (within last 4 weeks, wash-out allowed):
 
 1,25(OH)₂D₃ or an analogue (e.g. paricalcitol, hectorol) Calcimimetics (e.g. cinaclacet) Medications known to potentially induce or inhibit CYP24A1 or CYP3A4
EFFICACY EVALUATIONS	None
PRIMARY ENDPOINT	
 Metabolic clearance of labeled 25(OH)D₃ (administered dose/AUC)
SECONDARY ENDPOINTS	
 AUC of labeled 25(OH)D₃ Terminal half-life of labeled 25(OH)D₃ Volume of distribution in the central compartment of labeled 25(OH)D₃
OTHER EVALUATIONS	Metabolic formation clearance (metabolite/parent AUC ratio) for metabolites of labeled 25(OH)D ₃
SAFETY EVALUATIONS	
Change in the serum concentrations of calcium, creatinine, AST, and ALT and from baseline to 7 days after 25(OH)D₃ administration
 
Incidence of adverse events

PLANNED INTERIM ANALYSES	This is not a clinical trial with an efficacy outcome, and it is neither randomized nor blinded. Formal interim analyses are not planned.
STATISTICS Primary Analysis Plan	We will examine the distribution of D ₆ -25(OH)D ₃ clearance by CKD status (3 categories) and race (2 categories) using box plots and summary statistics. We will test associations of CKD status and race with D ₆ -25(OH)D ₃ clearance (continuous outcome variable) using linear regression. Models will be adjusted for age, gender, diabetes status, body size, baseline 25(OH)D concentration, and other covariates strongly related to 25(OH)D ₃ clearance. We will test whether associations of CKD status with clearance are modified by race by including a CKD x race interaction term.
Rationale for Number of Subjects	Our power calculations conservatively assume an interaction between CKD status and race, for which each cell in the 3x2 recruitment grid would require individual comparison. With this approach, we estimate that 17 people in each of two groups will provide 80% power to detect a difference in D ₆ -25(OH)D ₃ half-life of 2 days, assuming a standard deviation of 2 days. We will recruit 20 people per cell to allow for multivariable adjustment.

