11.2.1 Serious Adverse Experience Reporting

The PI will document all SAEs that occur (whether or not related to study drug) on an SAE Report Form. The collection period for all SAEs will begin after informed consent is obtained until all procedures for the final study visit have been completed.

All SAE Report Forms will be reviewed by the PI. SAE reports that are both related and unexpected will be sent to FDA within one business day of learning of the event. SAE reports that are both related and unexpected will also be forwarded to the UW Institutional Review Board, in accordance with UW Standard Operating Procedures. Because this is an observational study, no data safety and monitoring board will be created for this trial. Adverse events and recruitment will be monitored by the PI and reported to the UW IRB, as described above.

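### Section 11.4 item 3 can drop new kidney-related admissions from the AE and SAE counts, mainly in the eGFR <60 and hemodialysis groups, unless the investigator judges them a worsening or an increase in admissions

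*Combined protocol and SAP*

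**What the plan says.** Section 11.4 first makes any adverse event that leads to hospitalization an SAE, unless the protocol instructs otherwise. It then lists three exemptions under the lead-in "Neither the condition, hospitalization, prolonged hospitalization, nor surgery are reported as an adverse event in the following circumstances". Item 1 covers elective or diagnostic procedures for a pre-existing condition. Item 2 covers admissions needed for efficacy measurement. Item 3, with its one exception, reads "Hospitalization or prolonged hospitalization for therapy of the target disease of the study, unless it is a worsening or increase in frequency of hospital admissions"; whether the exception applies is left to the clinical investigator's judgement.

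The definitions it acts on are in Sections 11.1 and 11.2. For AEs: "An adverse event (AE) is any symptom, sign, illness or experience that develops or worsens in severity during the course of the study". For SAEs: "An SAE is defined as any AE occurring at any dose that results in any of the following outcomes", and the outcomes listed include "inpatient hospitalization or prolongation of existing hospitalization".

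On reporting, Section 11.2.1 states: "The PI will document all SAEs that occur (whether or not related to study drug"). It also says that no data safety monitoring board will be set up and that the PI monitors adverse events. The Synopsis lists "Incidence of adverse events" among the safety evaluations and gives efficacy evaluations as none. Section 2.1 says that participants receive no direct benefit, and Section 4 describes a single-dose PK study.

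**The concern.** A target-disease exemption has a purpose in a trial that treats a disease, where admissions for that disease are expected and are often captured as efficacy outcomes. Here nothing is treated and no efficacy outcome would pick up the exempted admissions. What the exemption removes from AE reporting, no other endpoint recovers.

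CKD status is the main exposure and a recruitment stratum, so the exemption does not fall evenly. Participants with eGFR <60 or on hemodialysis are the most likely to be admitted for kidney-related care. The rationale in Sections 1 and 2 also expects slower clearance of vitamin D metabolites in CKD. At stake is the completeness of the described AE and SAE incidence in those strata, and whether counts set out by stratum would be like for like.

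**Working it through.** The plan gives no figure for this point, so the check sets the rules side by side.

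**1. Which disease is meant.** No section defines it. CKD/ESRD fits best, because it defines the strata in the Synopsis and Table 6.1. Impaired vitamin D metabolism is another possible reading. That CKD is meant is therefore an inference.

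**2. What the exemption removes.** It covers the condition as well as the admission. Since Section 11.2 builds the SAE on the AE, an exempted event leaves both counts.

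**3. Where item 3 changes the outcome**, reading the target disease as CKD/ESRD:

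| Admission for kidney-related therapy | AE under 11.1? | After item 3 |
|---|---|---|
| Stable pre-existing disease, nothing new | No | No change |
| Judged a worsening | Yes | Still reportable |
| Judged an increase in admission frequency | Yes, if something develops or worsens | Still reportable |
| New unplanned episode, judged within the usual pattern | Yes, it develops during the study | Exempt, so lost |

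The AE definition has two arms: events that develop and events that worsen. The exception restores worsening and greater frequency, but not new episodes as such. The fourth row is the gap. If item 3 removed only events that were not AEs, it would do nothing; wherever it has an effect, it removes events that meet Section 11.1.

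**4. How the judgement is made.** It rests with the clinical investigator. No criterion for worsening and no reference period for frequency is given. Sections 9.1.3 and 10.2 require a full medical history at baseline but do not itemise past admissions. Section 11.2.1 provides no independent board.

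**5. Who is affected.** The eGFR <60 and hemodialysis strata are planned at 40 + 40 = 80 of 120. The third stratum is defined by eGFR ≥60 alone. Section 6.1 allows recruitment from a CKD cohort, and Section 2 reports an eGFR ≥60 category within that cohort. Kidney disease is therefore possible in the remaining 40.

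**6. Size.** Expected loss in a stratum = person-years × admission rate × share for kidney therapy × fraction f judged to be the usual pattern. Only the first term follows from the documents. For 40 hemodialysis participants over about 12 weeks on study it is 40 × 12 / 52 = 9.23 person-years; over the 8 weeks after dosing it is 40 × 8 / 52 = 6.15.

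Purely as an assumption, take 0.5 to 2 admissions per person-year and a 20% to 40% share:

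- After dosing: 6.15 × 0.5 × 0.2 = 0.6 to 6.15 × 2 × 0.4 = 4.9, times f.
- Whole 12 weeks: 9.23 × 0.5 × 0.2 = 0.9 to 9.23 × 2 × 0.4 = 7.4, times f.

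With f anywhere between 0 and 1, these are ceilings that can shrink to zero. They are not estimates.

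**The case against.** The strongest reply is that item 3 is a deliberate exception and a narrow one. Section 11.4 allows the protocol to instruct otherwise, and Section 11.2.1 covers all SAEs without redefining them. A reader might infer that 11.4 contradicts 11.2 and 11.2.1. It does not: it is an express carve-out, and that part of the reply stands.

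A reader might also infer that kidney-related admissions drop out wholesale. The documents do not support that either. Worsening or more frequent admissions stay reportable, stable disease was never an AE, and an admission for fluid overload or an electrolyte problem could readily be judged a worsening. Section 11.3 separately makes a laboratory abnormality needing active management an AE. The baseline history gives the investigator something to judge against, and worsening needs no frequency baseline. All of this narrows the gap to investigator discretion over new episodes.

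It does not close the gap. The exception omits events that develop without being judged a worsening. Section 11.3 does not reach an admission without a laboratory abnormality, and it does not say whether it prevails over an exemption that also covers the condition.

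Finally, no between-group safety comparison is specified; Section 14.1 only defines the safety set as all dosed participants. That limits the consequence to incomplete description, not a biased test.

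**Conclusion.** The point holds as a minor one. Item 3 is a poor fit for a study that treats no disease. It can remove new, unplanned kidney-related admissions from the AE and SAE counts on an investigator judgement that has no stated comparison period and no board to check it. This rests on reading the target disease as CKD/ESRD.

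The effect is concentrated in the strata planned at 80 of 120 participants. A reader might infer that it is confined to them and touches none of the other 40; the eGFR-only definition and the recruitment sources do not support that. A reader might also take the illustrative counts as a forecast. They are not one, because the documents give no admission rate, no share for kidney therapy and no basis for f.

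Nor does the exemption reach creatinine change or the other laboratory safety measures, which are scheduled at baseline and Day 7 whatever the admissions. The primary endpoint, clearance, and its analysis are untouched.

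**What to change.** Delete item 3 of Section 11.4. Item 2 has nothing to act on, since there are no efficacy evaluations, and can be removed at the same time as tidying. Keep item 1. State that an unplanned admission meeting the AE definition in Section 11.1 is recorded as an SAE in every stratum, with a flag for kidney-related admissions, and that relatedness to study drug is judged separately under Section 11.1.2. Deleting item 3 does not make every admission an SAE, because the AE definition must still be met.

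The cost is a short text change and a few more SAE forms for background kidney-related admissions. Section 16.2 sends SAEs to the IRB under its own procedures whatever their cause, so some of these may also be notified there. Expedited FDA reporting is unchanged, because Section 11.2.1 limits it to SAEs that are both related and unexpected.
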